#### **Blood-Glucose Meter**

An over-the-counter blood-glucose meter will be used to approximate levels of glucose in the blood to calibrate the Dexcom CGM System. The battery-powered blood glucose meter will consist of an on/off switch, a display, and an opening for test strips. Patients are expected to already own their own blood glucose meters as part of their normal standard-of-care. Patients who do not have a glucose meter will be provided one to use and keep following the study.

### Activity Tracker System

To help patients observe how physical activity impacts glucose levels, patients will be provided with a Fitbit Charge 2 wrist-worn activity tracker. This activity tracker will display in real-time the cumulative number of steps taken by the patient each day. The patient will also be able to view his/her step history via an app on the smartphone. The Fitbit activity tracker system consists of an activity tracker, a compatible charging cable, and an associated smartphone app that syncs step data to the Cloud.

Patients will be invited to wear the activity tracker from the start of the program.

Per protocol, patients will be asked to use their activity trackers for 10 weeks during the same period of CGM use. Afterwards, patients may be given the opportunity to use their activity trackers through August 31, 2018, if patients sync their tracker data at least once every three weeks. Patients will return the tracker and the smartphone at the end of the study.

### Training of site staff

Registered nurses will provide in-person assistance to patients in the application and use of the CGM. These nurses, along with program representatives, and all study staff interacting with patients will also be trained to answer any questions patients may have related to providing informed consent, and will be trained by the Sponsor in their respective roles. All research staff (excluding clinic staff) who interact with patients will receive training on the ethical treatment and safety of human research subjects.

## 7. Selection and Withdrawal of Subjects

Study participants will be recruited from UnitedHealthcare members in the Las Vegas area who are enrolled in a Medicare Advantage plan (Senior Dimensions®). To be eligible for the program, patients must meet specific inclusion/exclusion criteria. All Medicare Advantage patients who meet this criteria will be invited to participate in the program regardless of their latest A1C test.

We intend to enroll 500 program participants (defined as those to whom program materials and devices have been delivered). When 500 participants have been enrolled, any patients that have been recruited but who have not yet been enrolled (including those who may have signed a consent form) will be asked if they would like to be notified of any other upcoming study opportunities for which they may be eligible.

### Inclusion Criteria

To be included in the study, patients must:

- Be diagnosed with type 2 diabetes
- Be able to read, speak and understand English
- Have access to a telephone
- Have a Medicare Advantage plan through Senior Dimensions®

---

 The Fitbit may also record and display distance walked, calories burned, active minutes, hourly activity, stationary time, heart rate, and sleep stages, duration, and consistency; and contain tools to help users meet their personal health and fitness goals.

## Exclusion Criteria

Patients will not be eligible if any of the following criteria pertain to them:

- Pregnant
- Blind
- Deaf
- Receiving chemotherapy or radiation therapy to treat cancer (either now or within the last six months)
- Misusing any drugs (including alcohol, painkillers, hallucinogens, or others)
- Critically ill
- Diagnosed with or experiencing:
  - Kidney disease stages 4 and 5
  - End stage renal disease
  - Severe liver disease
  - Dementia
  - Schizophrenia
  - Bipolar disorder
  - Autism
  - An intellectual or learning disability
  - Arrhythmias other than atrial fibrillation
  - Congestive heart failure
- Has had a:
  - Myocardial infarction within the last 6 months
  - Stroke within the last 6 months
  - Stroke that resulted in significant disability (e.g., unable to write clearly or walk)

When a patient is referred to the program by the clinic and this patient is not eligible due to a diagnosis of congestive heart failure, one of the study's medical advisors will make a clinical judgement as to whether the severity of the patient's congestive heart failure warrants exclusion from the study.

Initial eligibility will be determined using medical and pharmacy claims data. Since these claims will not address all inclusion and exclusion conditions, patients will confirm their eligibility by reviewing the eligibility criteria provided in the consent packet and the consent form, and attesting to their eligibility by signing the consent form.

If during the study a patient's status changes such that s/he is no longer eligible to participate, the patient will be removed from the study and will be asked to return all devices (with the exception of used sensors, the used transmitter, and the glucometer if the patient received one).

## Patient Participation

All program participants will participate at-will and have the freedom to terminate their participation at any time. Participants, including those who intend to withdraw from the program or those who have withdrawn will be able to access program coaches for assistance with any program-related questions or issues.

During the time that patients use the CGM system, coaches will schedule weekly calls with them. If patients demonstrate by their actions that they no longer want to participate in the study by no longer syncing their CGM or activity tracker data, outbound call or text messaging efforts will be made to reach the patient. If after three weeks there has been no data received and no communication with the patient, a voicemail will be left asking patients to reply within three days or they will be considered dropped from the study. No response to these voicemails will result in the shipment to these patients of a postage-paid box and a letter. The letter will inform patients that they are considered as non-participating and need to return the CGM devices, activity tracker, and smartphone.

During the course of the program, should any participant report medical issues that may affect that patient's ability to participate in the program, the patient will be directed to consult with his/her physician.

## 8. Treatment of Subjects

This program will provide dedicated resources to assure informed consent.

Patients will be instructed to continue to follow the advice of their physicians, including taking prescribed medications.

Patients will sign and date an IRB-approved consent form that indicates that if they are injured from applying or wearing the CGM system or activity tracker in the course of the program that they will receive treatment and that their insurance may be billed. Copays and costs related to injuries from applying or wearing the CGM devices and activity tracker which are not paid for by patient's insurance will be covered by Savvysherpa (Sponsor). Charges for medical care will be based on insurance contracted rates and not mastercharge sheet prices.

Patients with medical concerns related to the study devices will be instructed to contact the study doctor and/or his staff for evaluation. Patients with any other health concerns will be encouraged to see their health providers, or if needed, seek emergency assistance as part of their normal standard of care.

Patients and study staff will be provided with the device manufacturers' technical assistance telephone numbers to report any device-related problems or concerns.

Patients will be provided with a program phone number to call and report other problems or concerns. Patients who need assistance with the application and use of the CGM system can call their coach or be scheduled for an educational class.

## 9. Assessment of Safety

While the proposed program is essentially educational in nature, every effort will be made to ensure that patients are using their devices properly. Should any concerns about patient safety arise, patients will be directed to see the study doctor or his staff, and if necessary, seek emergency medical assistance.

The Dexcom Continuous Glucose Monitoring System described in this protocol is considered by the Sponsor to be of non-significant risk as it does not meet the definition of a significant risk device per 21 CFR 812.3(m), in that CGM

- (1) Is not intended as an implant and presents a potential for serious risk to the health, safety, or welfare of a subject;
- (2) Is not purported or represented to be for a use in supporting or sustaining human life and presents a potential for serious risk to the health, safety, or welfare of a subject;
- (3) Is not for a use of substantial importance in diagnosing, curing, mitigating, or treating disease, or otherwise preventing impairment of human health and presents a potential for serious risk to the health, safety, or welfare of a subject; or
- (4) Otherwise does not present a potential for serious risk to the health, safety, or welfare of a subject.

Additionally, the system is being used in a manner not entailing significant risk, in that it is being used for educational purposes and as an adjunct to normal care.

The following information supports a non-significant risk determination for the device that will be used in this protocol:

- Chesapeake IRB has previously designated this CGM investigational device as a Non-Significant Risk device for our research protocol Pro00021722;
- FDA-approved Dexcom CGM Systems have been considered a non-significant risk device;
- The CGM devices used in this study are being used on-label in the intended population;
- The Medtronic-Minimed Guardian RT® CGMS, an FDA-approved device using similar technology, has been considered a non-significant risk device;
- The FreeStyle Navigator® CGMS, an FDA-approved device using similar technology, has been considered a non-significant risk device;
- The insertion needle thickness used in the device is not significantly thicker than the needles used in syringes for insulin injection and the potential needle insertion depth is less than 0.6 inches;
- None of the expected device-related adverse events as defined in the protocol and associated documents would be life-threatening or would result in any permanent impairment of a body function or permanent damage to a body structure;
- There are no expected electrical safety risks as the device has passed the electrical safety tests as per EN45502-1 and EN60601;
- If the subject feels any discomfort during the course of the study, he/she will be able to remove the device immediately (the device is not permanent);
- The device is being used to complement, not replace, self-monitoring of blood glucose meter information, and readings are not intended to be used alone to make diabetes self-management decisions. As with the currently approved device and per intended use of similar technologies, subjects in the study will be instructed not to use the device for diabetes therapy or management;

- Subjects will be instructed to monitor their blood glucose levels as per their usual practice.

Adverse events (AE) associated with the use of the device include pruritus (severe itchiness present 48 hours after removal), erythema (reddening of the skin present 48 hours after removal), and inflammation (swelling and pain, defined as 8 or greater on a 10 point scale 48 hours after removal) where the adhesive touches the skin; local infection at insertion site; and shooting pain located at the site of the sensor (defined as 8 or greater on a 10 point scale). Rarely, the sensor wire will fracture when the sensor is being inserted, worn, or removed. If a sensor breaks and no portion of it is visible above the skin, the participant will be instructed to not remove it and seek medical care from the study doctor and/or his staff.

No serious adverse events (SAE) or Unanticipated Problems (UP) are expected as a result of participation in this minimal risk study. However, AE, SAE and UP will be monitored in the following ways:

- Participants in the study will be instructed to call the study doctor's clinical research coordinator to report all AE, SAE and UP related to the use of the CGM devices. The study doctor and/or his staff will assess the severity of any health problems associated with the device, and if needed, see the patient at the study clinic to assure appropriate care.
- Study coaches will listen for any reports of AE or SAE or UP in the course of their communications with participants, and will connect reporting patients with the study doctor's clinical research coordinator so events can be assessed and documented and patients can receive care, if needed.
- Any reports of AE or SAE or UP received by Dexcom's Technical Support representatives will be documented and reported to the Sponsor. Coaches will then promptly notify the study doctor's clinical research coordinator of these reports so that the coordinator can then follow up with the patient to assess event severity and relatedness, and schedule the patient for care, if needed.

The Sponsor-Investigator will receive CGM-related AE and SAE and UP information from Dexcom through secure data transfers. AE and SAE and UP information from the study doctor will also be stored and transferred securely. Any other records pertaining to AE and SAE from patient conversations with program staff will be recorded and documented using call-management software and the patient's Case Report Form.

The Sponsor-Investigator will ensure proper reporting of AE and SAE and UP to Chesapeake IRB, the CGM manufacturer, the FDA, and any other regulatory bodies according to regulations and standard operating procedures. (See Appendix C for a chart illustrating the reporting process, and Appendix B for AE assessment guidance for coaches.)

Patients will be provided with a summary printout of their recorded CGM data at the end of their participation with CGM. Patients can request a summary printout anytime during the trial. Patients can share their CGM data with their providers.

The Standard of Care guidelines associated with the program direct patients to seek medical care when needed. Guidance exists within the guidelines to seek medical advice when glucose values are extremely high over long periods of time, fluctuate rapidly from high levels to low levels and vice versa, or a

pattern of low glucose values is present. Coaches will remind patients of these guidelines but will not give medical advice. Coaches can send summary CGM data to patients upon patient request.

Because the CGM data is an adjunct to patients' diabetes care, the investigator and research staff will NOT constantly monitor patients' realtime CGM data nor will research staff and coaches contact patients' medical providers on behalf of patients when low or high CGM values are observed. Patients will be responsible for using the blood glucose meter to manage their diabetes and to seek medical attention when needed.

Episodes of hyperglycemia or hypoglycemia that require patients to seek medical attention will be considered an AE or SAE depending upon the situation.

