#### Skin Redness or Rash – Severity Category

1. On a scale of 1 to 10, where 1 is very little, and 10 is severe, how would you rate the redness of your skin or rash?
  - If 1-5, do not record as AE, **unless itchiness and/or pain are moderate**
  - If 6-7, Mild AE
  - If 8-9, Moderate AE**
  - If 10, Severe AE**
2. Are you experiencing **pain or itchiness** where your skin is red or where you have a rash?
  - If no, stop.
  - If yes, on a scale of 1 to 10 where 1 is very little, and 10 is severe, how would you rate the **itchiness**?
    - If 1-5, do not record as AE
    - If 6-7, Mild AE
    - If 8-9, Moderate AE**
    - If 10, Severe AE**

- If yes, on a scale of 1 to 10 where 1 is very little, and 10 is severe, how would you rate the **pain**?
  - If 1-2, do not record as AE
  - If 3-5, Mild AE
  - If 6-8, Moderate AE**
  - If 9-10, Severe AE**

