#### **Insertion Site Pain or Discomfort – Severity Category**

1. On a scale of 1 to 10, where 1 is very little, and 10 is severe, how much does your pain or discomfort affect your ability to do your daily activities?
  - If 1-2, do not record as AE
  - If 3-5, Mild AE
  - If 6-8, Moderate AE**
  - If 9-10, Severe AE**

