### **Detached/Broken Sensor Wire – Severity Category**

1. Do you see the sensor wire sticking out of your skin?
  - If no, then stop
  - If yes, then ask: On a scale of 1 to 10, where 1 is very little, and 10 is severe, how would you rate your pain or discomfort
    - If 1 – 7, **then Mild AE**
    - If 8 – 9, **then Moderate AE**
    - If 10, **then Severe AE**

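### Section 9 and the coach scripts in Appendix B define the same sensor-site reactions as adverse events by different criteria, and no visible text says which governs

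*Combined protocol and SAP*

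**What the plan says.** Section 9 (Assessment of Safety) names the AEs associated with the device. Three are skin reactions under the adhesive. Itch counts if it is severe and still there two days after the sensor comes off. Redness counts on presence at that time alone: "erythema (reddening of the skin present 48 hours after removal". The third reaction needs a score as well: "inflammation (swelling and pain, defined as 8 or greater on a 10 point scale 48 hours after removal". A fourth AE is felt at the sensor itself: "shooting pain located at the site of the sensor (defined as 8 or greater on a 10 point scale". Local infection at the insertion site is also listed. Section 9 gives no mild, moderate or severe grades.

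In Appendix B, coaches match a complaint to a type, ask scripted questions scored 1 to 10, and then grade severity and relatedness:

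- **Insertion-site pain.** The coach asks "how much does your pain or discomfort affect your ability to do your daily activities". Scores of 1-2 are not recorded, 3-5 is mild, then "If 6-8, Moderate AE", and 9-10 is severe.
- **Redness or rash.** Scores of 1-5 are not recorded "unless itchiness and/or pain are moderate"; 6-7 is mild, 8-9 moderate, 10 severe. Itch at the red area has its own item with the same bands from 6. Pain at the red area has an item with the insertion-site pain bands, starting at 3.
- **Itchiness and swelling.** For each, 1-5 is not recorded and 6 upward is an AE.

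None of these severity scripts has a 48-hour condition. The relatedness scripts for redness, itch and swelling rate a site where a sensor sat within two days as possibly related, and one where it sat two or more days earlier as probably not related.

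Section 9 has the study doctor or staff assess severity, names no scale for them, and cites Appendix B as guidance for coaches. Nothing visible says which set of definitions prevails.

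**The concern.** The protocol contains two stated rules for what counts as a device AE, and they can classify the same complaint differently. The device is not FDA-approved (Section 3). Section 9 commits the sponsor-investigator to report AEs to the IRB, the manufacturer and the FDA. Part of its argument for non-significant risk also rests on the expected device AEs as the protocol and associated documents define them, and those definitions do not agree.

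The mismatch runs in both directions. A coach following the script would record pain that falls below the Section 9 cut-off. The same coach would leave unrecorded a low redness score that Section 9 lists if the redness is still present at 48 hours. A table built from such records, for the planned 500 participants, would mix two case definitions.

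**Working it through.** The plan gives no AE figure to reproduce. The check sets the two definitions side by side, score by score from 1 to 10.

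| Reaction | Section 9 | Appendix B | Score range in conflict |
|---|---|---|---|
| Pain | shooting pain, 8 or more | AE from 3 (insertion-site script, and pain item of the redness script) | 3-7 |
| Swelling | inflammation (swelling and pain), 8 or more, at 48 h | AE from 6, any time | 6-7 |
| Redness | present at 48 h, no score | AE from 6, any time; 1-5 unrecorded unless itch or pain is moderate | not comparable by score |
| Itch | severe at 48 h, no score | AE from 6, any time | not comparable by score |

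**Pain.** Scores that qualify under Section 9: 10 − 8 + 1 = 3. Scores that qualify in the script: 10 − 3 + 1 = 8. Scores that qualify only in the script: 8 − 3 = 5, namely 3, 4, 5, 6 and 7.

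**Swelling.** Section 9: 3 scores. Script: 10 − 6 + 1 = 5. Scores that qualify only in the script: 5 − 3 = 2, namely 6 and 7. In addition, swelling of 8 or more that has resolved by 48 hours is an AE in the script and does not meet Section 9.

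**Redness.** A score of 1-5 still visible at 48 hours meets Section 9 but is left unrecorded by the script unless itch or pain is moderate. A score of 6 or more that clears before 48 hours is the reverse.

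**Itch.** Section 9 does not say which score is severe, so discordant scores cannot be counted. The timing difference is the same as for redness: itch of 6 or more that clears before 48 hours is an AE in the script only.

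**Relatedness.** The Section 9 entries for redness, itch and inflammation require persistence to 48 hours, which is two days, after removal. A reaction that meets this timing lies at or beyond the boundary between possibly related and probably not related in Appendix B. One that continues past 48 hours falls on the probably-not-related side, although Section 9 lists it as device-associated.

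**Within the redness script.** Redness of 1-5 with pain of 3-5 meets two instructions. The redness item says not to record, because pain is not moderate until 6. The pain item gives a mild AE. The script does not say whether these are one event or two.

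**The case against.** Several defences have force.

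- **The terms are not identical.** Shooting pain is narrower than pain or discomfort, and swelling with pain is narrower than swelling. The insertion-site script scores interference with daily activities, not intensity. The counts of 5 and 2 scores therefore compare neighbouring concepts. This weakens the pain comparison, but the pain item in the redness script does ask for intensity and also starts at 3. Narrower terms also do not account for the missing 48-hour condition.
- **Section 9's list is open-ended.** It says what AEs include. Even so, it fixes cut-offs for the events it names.
- **The scripts are only guidance, and Section 9 has coaches connect reporters with the coordinator.** That is so, but Appendix B also tells coaches to determine severity and not to record some scores.
- **Much of the data is already captured.** Coaches document answers in templates, and the relatedness items ask where the sensor was. This stands, and it makes the fix cheap.
- **Relevant material is not visible.** The red highlighting, the Appendix C chart and the Anticipated Complaints Guidebook could bear on routing and final adjudication.

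A reader might go further and infer four things that the documents do not support:

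- That participants who talk to coaches will show more pain AEs and fewer redness AEs than those who call the clinic. No text says that clinic staff or the manufacturer's support line apply the Section 9 cut-offs.
- That subgroup or engagement comparisons will be distorted. Section 10 plans no AE comparison; its subgroup analyses concern adoption, participation, behavior and diabetes markers.
- That the different grading of pain in the broken-wire script is a contradiction. A broken wire is a different event and may be graded separately.
- That the redness script contradicts itself. It can be read as grading redness and pain as separate events, so it needs clarifying, no more.

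**Conclusion.** The inconsistency is real. Section 9 and Appendix B set incompatible criteria for the same group of sensor-site reactions, and no visible text ranks one above the other. On score alone, the conflict covers pain of 3 to 7 and swelling of 6 or 7, subject to the difference in terms. For redness and itch it lies in the kind of criterion, and for relatedness in the treatment of reactions lasting past 48 hours.

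AE counts therefore depend on which definition is applied. How much they would move cannot be computed, because the documents give no distribution of scores or of time to resolution, and the shares of the scale above should not be read as shares of complaints. Nothing here shows an effect on serious AE or unanticipated-problem reporting, or on the study's primary aim. This is a consistency fix, worth making because it is cheap and the device is unapproved.

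**What to change.** Reconcile the AE paragraph of Section 9 with the severity and relatedness scripts in Appendix B for redness, itch, insertion-site pain and swelling, so that there is one case definition. State that it governs for coaches and for the study doctor's staff. This review takes no view on which cut-offs or timing are right.

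For every complaint, including those below the cut-off, record:

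- the raw 1-10 score;
- whether a sensor was in place or, if not, the days since removal;
- the reporting route.

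Build the AE table from these fields with the single definition. In the redness script, state whether pain of 3-5 with redness of 1-5 is recorded as a separate pain AE.

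The cost is one revised paragraph, a small script revision and a few form fields. Coaches already ask for the score and the sensor location. The downside is that minor complaints will be logged even when they do not count as AEs.

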#### [Integration with patient care](#)

Throughout the program, patients will be instructed to follow their normal care plan as directed by their physicians and as consistent with ADA 2017 standard-of-care guidelines. This includes taking medications as prescribed; engaging in physical activity—especially walking after meals; eating a diet that optimizes glucose control through food choice and timing; responding to hypoglycemia symptoms with a fingerstick and consuming a pre-determined amount of glucose; and monitoring emotional wellness. By providing a continuous graph of each participant's glucose, the CGM system illustrates how the above-described glucose management behaviors impact the participant's glucose.

Should patients in the course of the program experience any health problems associated with the use of their CGM devices, they will be directed to contact the study doctor's clinical research coordinator. The coordinator will assess the severity and relatedness of the event and arrange for appropriate care. Should patients mention a potential study-related health concern to their coach, the coach will actively work to assure the patient speaks with the study doctor, either through a warm transfer or callback.

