### Risks of the Activity Tracker Device

The Fitbit has a wrist band. Skin irritation from these devices is a remote possibility (there are very few reports in the online literature regarding this occurrence with similar devices). Study participants who experience skin irritation will be instructed to remove the activity tracker during sleep, and/or to alternate wearing it on the opposite wrist. There is also a slight risk that the privacy of the activity tracker data could be exposed if an unauthorized source hacks into the activity tracker's data system. Due to security and authorization that Savvysherpa has in place this risk is minimal.

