## 23. Appendix B

### Adverse Events Severity and Relatedness Questions

May 2017

When patients share a complaint, program coaches will identify the complaint in the Anticipated Complaints Guidebook. Based on the complaint type, coaches will then ask questions to determine:

1. Severity of the complaint (e.g., Mild, Moderate, or Severe), and
2. Relatedness of the complaint to the use of program devices (e.g., Not Related, Probably Not Related, Possibly Related, and Probably Related)

Coaches will document answers in the templates provided, including the Adverse Event document.

If the complaint falls in any of the severity categories highlighted in red, the coach will make a “warm transfer” to the study doctor and/or his staff so that the patient can be scheduled for an ancillary appointment.

If the complaint is an emergency, patients will be instructed to call 911.

If a patient has a complaint that is not listed in the Anticipated Complaints Guidebook, the coach can “warm transfer” the patient to the study clinic for guidance. The coach will document as much as possible in Adverse Event document. Follow up with the clinic will determine severity and relatedness.

Coaches will contact the PI when situations arise that are not covered in the Anticipated Complaints Guidebook.

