#### **Skin Redness or Rash – Relatedness Category**

1. Where is the location of the redness or rash?
  - If in the same location as the sensor on your skin, then Probably Related
  - If in a location where a sensor was within 2 days, then Possibly Related
  - If in a location where a sensor was 2+ days in the past, then Probably Not Related
  - If in a location where a sensor was never placed, then Not Related

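### Appendix B's redness and itchiness scripts would code a reaction under the activity-tracker band as Not Related, and two participant reporting instructions are narrower than the rest of the plan

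*Combined protocol and SAP*

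**What the plan says.** **Instructions to participants.** Section 9 has participants call the study doctor's clinical research coordinator to "report all AE, SAE and UP related to the use of the CGM devices". Section 6 (Integration with patient care) directs them to the same coordinator for "any health problems associated with the use of their CGM devices". Both name the CGM devices only.

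**Broader provisions.** Section 8 says: "Patients with medical concerns related to the study devices will be instructed to contact the study doctor and/or his staff for evaluation". It also commits the sponsor to uninsured costs of "injuries from applying or wearing the CGM devices and activity tracker". Section 6 adds: "Should patients mention a potential study-related health concern to their coach, the coach will actively work to assure the patient speaks" with the study doctor. In Section 9, coaches listen for adverse events of any kind and connect the patient with the coordinator. Other AE records from patient conversations go into the call software and the Case Report Form.

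**Relatedness.** The opening of Appendix B gives coaches the task of determining "Relatedness of the complaint to the use of program devices". In the script for redness or rash, the last of the four location answers is: "If in a location where a sensor was never placed, then Not Related". The itchiness script ends the same way.

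**Tracker risk.** Section 12 says of the wrist-worn tracker: "Skin irritation from these devices is a remote possibility".

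**The concern.** Every participant receives two body-worn devices, a CGM sensor and a wrist tracker. The plan foresees skin reactions from both and says relatedness is to be judged against program devices. A script that recognizes only one of the two cannot do that for the other. A coach who applies it correctly will still record the wrong answer for a tracker-band reaction.

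The CGM-only wording adds to this. A participant with a sore wrist, or one hurt while walking after a meal as coached, is not told by Section 9 or by the Section 6 direction that this is something to report.

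What is at stake is the accuracy of the AE record for a program that combines CGM, tracker and coaching and is meant to inform a larger study. Section 10 specifies no safety analysis, so no planned estimate is biased. The harm is to the record and to anything later drawn from it.

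**Working it through.** No arithmetic model applies, and the plan has no figure of its own to reproduce. The check is a reading of every relatedness script, a trace of one event, and a comparison of the reporting routes.

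**1. The scripts.** Appendix B has eight relatedness scripts: redness or rash, itchiness, insertion-site pain, swelling, bruising, bleeding, infection, and broken sensor wire.
- Using sensor location only: 8 of 8.
- Ending in Not Related where no sensor was ever placed: 7 of 8. The broken-wire script offers only Probably Related.
- Mentioning the tracker, the wrist or physical activity: 0 of 8.

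Six of the eight concern the sensor wire or its insertion site, where sensor location is the right question. The gap matters in the other two, redness or rash and itchiness, because either device can cause those complaints.

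**2. One event traced.** A participant tells the coach of a rash under the tracker band.
- The complaint has its own script, so the coach uses it.
- Suppose redness is rated 6. The severity script makes that a mild AE.
- The location question follows. Section 6 places the sensor on the abdomen and the tracker on the wrist. The answers for a current sensor site, a site used within 2 days, and a site used longer ago all fail.
- The remaining answer is that no sensor was ever there. The code is Not Related.

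Itch at the same site follows the same path.

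**3. Possible rescues.** Appendix B lets the clinic settle relatedness for complaints missing from the Anticipated Complaints Guidebook. Rash and itch have scripts, so that route is not clearly triggered. Appendix B's mandatory transfer depends on severity category, so a milder event might keep the coach's code under that appendix alone. Section 9, however, has coaches connect reporting patients with the coordinator for assessment, which gives a chance of correction.

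**4. Reporting routes side by side.**
- CGM only: the Section 6 direction to participants and the Section 9 instruction to participants.
- Broader: Section 8 (study devices), the Section 6 coach route (study-related concerns), Section 9 coach listening and record-keeping, and the Appendix B unlisted-complaint route.

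**5. Activity-related injuries.** Walking after meals is a coaching objective in Section 6. An injury mentioned to a coach falls within Section 9's general listening. Because no script covers it, the coach can also transfer it to the clinic under Appendix B. The coach is permitted, not required, to transfer, and Appendix B frames relatedness around device use. No passage names such injuries as reportable or says how to judge their relation to the coaching.

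**The case against.** The strongest reply is that the Section 9 instruction is one of three monitoring routes listed there, and the others are not tied to participants' own CGM reports. Coaches are scheduled to call weekly during CGM use and listen for any event. Concerns about study devices go to the study doctor. Episodes of high or low glucose that need medical attention count as adverse events without any device link. Appendix B is described in Section 9 as guidance for coaches, and Section 6 has the coordinator assess severity and relatedness. Concentrating on an investigational CGM system rather than a wrist tracker is also a defensible emphasis.

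Most of this stands, and it rules out three stronger readings.
- A reader might infer that adverse-event reporting as a whole covers only CGM events. Sections 6, 8 and 9 contradict that.
- A reader might infer that walking injuries go unreported. They are not solicited, but the coach and unlisted-complaint routes can capture them.
- A reader might infer that tracker-related events must come out as zero. The documents do not show that the coach's code is final.

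What the reply does not remove is the wrong answer in the two scripts. Emphasis on the CGM does not explain it, because Appendix B itself states the wider purpose. A later correction by the coordinator is possible, but nothing in the text prompts it.

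**Conclusion.** The point holds in a limited form. Two Appendix B scripts, applied as written, give a tracker-band reaction a first-pass code that conflicts with the appendix's stated purpose. Two participant instructions are narrower than Section 8 and the coach provisions of Section 9. Activity-related injuries have a possible route into the record but no explicit reporting instruction or relatedness rule.

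The size cannot be given as a count. The plan intends to enroll 500 participants but states no rate of tracker reactions, and Section 12 expects few. Redness or itch rated 1 to 5 is generally not recorded as an adverse event, so many mild wrist reactions would never be classified as recorded AEs. The number miscoded may be small.

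The conclusion assumes that coaches follow the scripts literally and that the Guidebook adds no tracker question. The Guidebook is not supplied as a separate document, the Appendix C chart is not shown, and the red highlighting in Appendix B did not survive text extraction. Any of these could narrow the gap.

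**What to change.** - **Appendix B, redness or rash and itchiness scripts.** Add to the location question an answer for a current or recent tracker site that leads to a related category. Limit the final answer to places where neither a sensor nor the tracker has been. The existing grading by time since sensor wear could serve as the pattern.
- **Section 9 and Section 6 (Integration with patient care).** Reword the two CGM-only instructions to cover events related to any study device or program activity, in line with Section 8, the coach provisions of Section 9, and Appendix B. Change both, since editing one leaves the other in conflict.
- **Appendix B, opening text.** Add a line stating how relatedness is judged for injuries during program-encouraged activity, for example by clinic determination through the existing unlisted-complaint route.

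These edits change what is recorded and how it is coded, not how patients are managed. The cost is a few lines of text, a short update for coaches, and a few more AE forms.
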